#### 6.1.4.5 Duration of Response

##### Duration of Overall Response

The duration of overall response is measured from the time measurement criteria are met for CR or PR (whichever is first recorded) until the first date that recurrent or progressive disease is objectively documented (taking as reference for progressive disease the smallest measurements recorded since the treatment started).

The duration of overall CR is measured from the time measurement criteria are first met for CR until the first date that progressive disease is objectively documented.

##### Duration of Stable Disease

Stable disease is measured from the start of the treatment until the criteria for progression are met, taking as reference the smallest measurements recorded since the treatment started, including the baseline measurements.

To be assigned a status of stable disease, measurements must have met the stable disease criteria at least once after study entry at a minimum interval of 8 weeks.

Rev. 7/15

## 7. Study Parameters

### 7.1 Therapeutic Parameters

7.1.1 To be completed within 14 DAYS before randomization:

- All blood work, including pregnancy test.

7.1.2 To be completed within 28 DAYS before randomization:

- CT or MRI should be performed.

Rev. 2/14,  
6/14

	≤ 4 weeks Prior to Randomization	Day 1 of each cycle	Every 3 cycles	End of Treatment	Post Treatment to 5 years from study entry
Tests & Observations					
History and Progress Notes 	X	X		X	X
Physical Examination 	X	X		X	X
Pulse, Blood Pressure 	X	X			
Weight/BSA 	X	X			
Performance Status 	X	X			
Tumor Measurements 	X		X	X	X 
Adverse Event Assessment		X		X	X
Laboratory Studies					
CBC, Diff, Platelets 	X 	X			
Serum Electrolytes and Chemistry 	X 	X		X 	
Tumor markers 	X 		X		
Pregnancy Test (serum or urine HCG)	X 				
CT Scan and/or MRI 	X		X	X	X 
Specimen Submissions					
MANDATORY: Tumor Tissue FFPE 					
Peripheral blood, ACD or EDTA tube 	X				

1. Monitor for survival every 3 months until patient is two years from randomization, then every 6 months until patient is 5 years from randomization. Follow-up is no longer required after patient is more than 5 years from randomization. Once the patient progresses, adverse event assessments no longer need to be performed.

Rev. 6/14 2. Serum electrolytes: Na+, K+, bicarbonate, Cl, BUN, creatinine, glucose; total bilirubin, SGOT(AST), SGPT(ALT), alkaline phosphatase, albumin, total protein, calcium. Serum electrolytes and chemistry must be done within 1 week of start of Cycle 1 and ≤ 72 hours prior to each subsequent treatment cycle.

3. Within 2 weeks of randomization for women of childbearing potential.

4. Labs and physical exam must be done within 1 week of start of Cycle 1. After Cycle 1, Day 1, the start of each treatment cycle may be scheduled up to three days after the expected Day 1 of that cycle. History and Progress Notes; Physical Examination; Pulse, Blood Pressure; Weight/BSA; Performance Status; CBC, Diff, Platelets; Serum Electrolytes and Chemistry, and Adverse Event Assessment must be done ≤ 72 hours prior to each treatment cycle.

5. If only MRI of the abdomen and/or pelvis is available, this can be substituted for CT of abdomen and/or pelvis, but CT of chest should still be obtained. Copies of all standard-of-care imaging studies are to be submitted to the American College of Radiology Imaging Network (ACRIN) and the ACR Imaging Core Lab as outlined in Section [10](#).

6. Must be done within 2 weeks prior to randomization.

7. Post treatment scans will be performed every 3 months for 3 years from randomization and every 6 months between 3-5 years from randomization. The collection of tumor markers is encouraged at this time, but not required. Once there is confirmation of progression, scans and tumor measurements no longer have to be performed.

Rev. 6/14 8. Representative tumor tissue (block preferred) and related pathology reports are to be submitted for central diagnostic review and classification and defined research studies within 4 weeks following randomization as outlined in Section [11](#). Failure to submit the required materials may render the case unevaluable but will not impact patient participation in the trial.

9. Research blood sample may be collected at any time during the trial, although prior to start of treatment is preferred. EDTA may be used if ACD not available. Submit from patients who answer "Yes" to "I agree to provide additional blood for research" as outlined in Section [12](#).

Rev. 6/14 10. Imaging instructions: All standard-of-care imaging studies (including CT, MRI, PET, perfusion CT, or any combination) of the abdomen and pelvis will be submitted to ACRIN via the ACR Imaging Core Lab per Section [10.2](#) instructions. Submission of chest images is optional. Preferably, a minimum of three (3) image phases will be submitted (see below):

Preferred:

- Late arterial phase through the abdomen
- Portal venous phase through the abdomen and pelvis
- Delayed (equilibrium) phase through the abdomen at 3 to 4 min after contrast administration.

If performed per standard institutional practice:

- Perfusion CT sequences of an area of interest is optional and should be performed according to site specific specifications if available at the participating institution.

11. Tumor markers: Chromogranin A and Neuron Specific Enolase (NSE) are required at baseline and every 3 cycles. Other tumor markers may be done at the investigator's discretion and based on patient symptoms (i.e. glucagon, insulin, VIP, pancreatic polypeptide, gastrin). Continued collection of tumor markers is encouraged during the follow-up period.

Rev. 2/14, 6/14 12. End of Treatment assessments and labs must be performed within 4 weeks after patient's last date of protocol treatment. CT scan and/or MRI performed within 30 days of the last date of protocol treatment do not need to be repeated at End of Treatment.

Rev. 6/14

13. After randomization, the CT scan or MRI, Tumor Measurements, and Tumor Markers will be completed every 3 cycles. Should the 3 cycle interval be delayed or extended, the next interval scan and tumor markers should be completed no more than 16 weeks from previous scan ( $\leq$  4 weeks from planned scan date).

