## 5. Treatment Plan

### 5.1 Administration Schedule

One cycle = 28 days

All doses are based on actual weight. If there is a  $< 5\%$  change in Body Surface Area (BSA), keep the doses the same. If there is a  $\geq 5\%$  change in BSA, a new dosing weight and BSA should be set and used for dose calculations.

- Temozolomide
  - The temozolomide dose will be capped at 400 mg daily. The calculated dose by BSA will be rounded down to minimize the number of capsules required. The treating investigator should use their best judgment to meet these guidelines.
  - Temozolomide should be taken by mouth at night after fasting from solid food for two hours. Temozolomide capsules must not be crushed and must be administered whole.
  - Temozolomide missed doses will not be made up and patients should not double-up on missed doses during treatment.
  - Ondansetron or other anti-emetic is strongly suggested as a premedication 30-60 minutes prior to temozolomide. Otherwise, anti-emetics, anxiolytics, and analgesics may be provided at physicians' discretion.
- Capecitabine
  - The calculated total daily capecitabine dose by BSA will be rounded down to allow doses using 500 mg tablets. Investigators should approximate the calculated dose based on the pill size available while rounding down to minimize the number of capsules required. The treating investigator should use their best judgment to meet these guidelines.
  - Capecitabine should be taken morning and night, with at least 8 hours between each dose. Capecitabine tablets should be swallowed with water within 30 minutes after a meal.
  - Capecitabine missed doses will not be made up and patients should not double-up on missed doses during treatment.

**NOTE:** Monitor CBC and platelet count prior to drug administration.

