### 5.2.2 Terminology

- **Adverse Event (AE):** Any untoward medical occurrence associated with the use of a drug in humans, whether or not considered drug related. Therefore, an AE can be **ANY** unfavorable and unintended sign (including an abnormal laboratory finding), symptom, or disease temporally associated with the use of a medicinal product, whether or not considered related to the medicinal product.
- **Attribution:** An assessment of the relationship between the adverse event and the protocol treatment, using the following categories.

ATTRIBUTION	DESCRIPTION
Unrelated	The AE is clearly NOT related to treatment
Unlikely	The AE is doubtfully related to treatment
Possible	The AE may be related to treatment
Probable	The AE is likely related to treatment
Definite	The AE is clearly related to treatment

- **CTCAE:** The NCI Common Terminology Criteria for Adverse Events provides a descriptive terminology that is to be utilized for AE reporting. A grade (severity) is provided for each AE term.
- **Expectedness:** Any adverse event, the type or severity of which is consistent with the current investigator's brochure, product label, and/or the protocol document

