8.1.10 Side Effects  
Hematologic: anemia, neutropenia, thrombocytopenia, aplastic anemia.  
Constitutional: fatigue, anorexia, weight loss  
Dermatologic: rash, pruritus, Stevens-Johnson-Syndrome  
Gastrointestinal: nausea, vomiting, constipation, diarrhea, abdominal pain, stomatitis, dysphagia  
Infections: PCP infection  
Metabolic: hyperglycemia, liver or kidney abnormalities  
Neurologic: headache, somnolence, insomnia, blurred vision  
Oncologic: secondary malignancy  
Psychiatric: anxiety, depression

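### No blood count is required after a patient's final cycle, although chemistry and adverse event assessment are, so hematologic toxicity may be under-recorded

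*Combined protocol and SAP*

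**What the plan says.** - **Calendar, section 7.1.** The row "CBC, Diff, Platelets" is marked before randomization and on the first day of each cycle. Its End of Treatment and Post Treatment cells are blank. The row "Serum Electrolytes and Chemistry" has the same marks plus one at End of Treatment, carrying note 12. Adverse event assessment, history and physical examination are marked at End of Treatment and afterwards.
- **Note 4, section 7.1.** On-treatment counts are timed to the next cycle: "CBC, Diff, Platelets; Serum Electrolytes and Chemistry, and Adverse Event Assessment must be done ≤ 72 hours prior to each treatment cycle".
- **Note 12, section 7.1.** "End of Treatment assessments and labs must be performed within 4 weeks after patient's last date of protocol treatment". The note does not say which labs.
- **Note 1, section 7.1.** Follow-up for adverse events ends at progression: "Once the patient progresses, adverse event assessments no longer need to be performed".
- **Sections 5.1, 8.1.11.1 and 8.2.11.1.** The general instruction also looks forward to a dose: "Monitor CBC and platelet count prior to drug administration".
- **Section 8.1.10.** Temozolomide's side-effect list opens with "Hematologic: anemia, neutropenia, thrombocytopenia, aplastic anemia". Section 8.2.10 opens capecitabine's list with anemia, neutropenia and thrombocytopenia.
- **Section 5.2.2.** An adverse event includes any "unfavorable and unintended sign (including an abnormal laboratory finding), symptom, or disease temporally associated with the use of a medicinal product".
- **Sections 2.2.3 and 9.4.** Toxicity is a secondary objective, and 9.4 states the precision of adverse event rates with at least 69 patients per arm.

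**The concern.** Each rule that calls for a blood count is attached to a dose about to be given. After the last cycle no dose follows, so none of these rules applies. Chemistry is nevertheless drawn at End of Treatment, and the plan gives no reason for leaving out the count.

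A low neutrophil or platelet count without symptoms is an adverse event under section 5.2.2, but it is found only if blood is drawn. What is at stake is how complete the hematologic part of objective 2.2.3 and the rates in section 9.4 are. Counts taken ad hoc after the last cycle would also vary from site to site. The weakest case is a patient who stops after one cycle with no draw before a second. That patient has no required count after any dose.

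**Working it through.** **1. The rules side by side.**

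| Source | Count tied to | Reaches past the last cycle? |
|---|---|---|
| Calendar row, 7.1 | First day of each cycle | No |
| Note 4, 7.1 | 72 hours before a cycle | No |
| 5.1, 8.1.11.1, 8.2.11.1 | Before drug is given | No |
| 5.3.2 (temozolomide) | Lowest counts of the previous cycle, to set the next dose | No |
| Note 12, 7.1 | End of Treatment, unspecified labs | Unclear; only chemistry is marked |

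**2. The plan's own figures.** The plan gives no number on this point. The precision figures in section 9.4 do reproduce for n = 69: the chance of at least one event at a true rate of 3% is 1 − 0.97^69 = 0.878 (stated: at least 87%), and the widest exact 90% interval is 20.9 points (stated: no wider than 21). Neither depends on when counts are drawn.

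**3. How many final cycles are affected.** Inputs from the plan are median PFS of 9 and 14 months (9.3), 28-day cycles with a maximum of 13 (5.1), and scans after cycles 3, 6, 9 and 12 (10.1.2). Assumptions are exponential PFS, progression acted on at those scans, and no other reason for stopping.

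One cycle is 28/30.4375 = 0.920 months, and S(t) = exp(−ln 2 × t / median).

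| | Arm A | Arm B |
|---|---|---|
| S at 3 cycles | 0.809 | 0.872 |
| S at 6 cycles | 0.654 | 0.761 |
| S at 9 cycles | 0.529 | 0.664 |
| S at 12 cycles = share starting cycle 13 | 0.427 | 0.579 |
| Stopped at first scan, 1 − S(3 cycles) | 0.191 | 0.128 |
| Mean cycles = 3(1 + S3 + S6 + S9) + S12 | 9.40 | 10.47 |

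Of 69 patients per arm, 69 × 0.427 ≈ 29 and 69 × 0.579 ≈ 40 would complete 13 cycles. None of them has a required count afterwards.

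**4. Share of all cycles with no required count after them.**
- If only completers are affected: 0.427/9.40 = 4.5% in Arm A and 0.579/10.47 = 5.5% in Arm B.
- If everyone stopped at a scan also skips the next pre-cycle count: 1/9.40 = 10.6% and 1/10.47 = 9.6%.

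The documents do not say whether that pre-cycle count is drawn, so these pairs are a lower and an upper case within the model.

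**5. Share within one patient.** It is 1/13 = 7.7% of cycles for a completer, 1/3 = 33.3% for a patient who stops after three cycles, and all of them for a patient who stops after one.

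**The case against.** A reader might infer that every patient's final-cycle myelosuppression goes unmeasured and undetected. The documents do not support that, for four reasons.

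- History, physical examination and adverse event assessment are required at End of Treatment and continue afterwards, the last until progression. Symptomatic cytopenia, or an abnormal count from routine care, would be recorded.
- Patients stopped under the hematologic hold rules (5.3.1 to 5.3.3) will usually have a count after their last dose, because a count triggers the hold. A patient who presents for a cycle that is then withheld may also have the count due within 72 hours before it. The most consequential cytopenias are therefore the least likely to be lost.
- Note 12's mention of labs could be read to include a blood count, and nothing forbids one.
- Section 5.3.2 presupposes counts within a cycle. In Arm B the instruction to check counts before drug is given could also be read as a count before temozolomide on day 10. That count would precede the final cycle's temozolomide, so it does not measure that drug's effect in the cycle.

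The size also needs care. About 10% is a share of cycles, whereas section 9.4 concerns rates per patient. A patient's worst grade changes only if the final cycle is worse than every earlier measured one, and a completer has 12 measured cycles behind them. Both arms follow the same calendar, and section 9.4 says that formal comparison of toxicity is not a goal.

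Finally, the calendar was read from a PDF, and its mandatory tumor tissue row shows no mark in any column, so a lost cell cannot be excluded. The blank count cells do agree with note 4, and the adjacent chemistry row kept its End of Treatment mark, so a loss is unlikely.

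These points narrow the claim. They do not supply a required count after the last cycle.

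**Conclusion.** The gap is real and limited. As written, the plan requires no blood count after the final cycle, while chemistry and adverse event assessment are required at End of Treatment. Asymptomatic final-cycle cytopenia may be missed and hematologic toxicity under-recorded. This applies mainly to patients who complete 13 cycles (about 43% of Arm A and 58% of Arm B) and to those who stop early without another pre-cycle draw.

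Under the stated assumptions final cycles are up to about 10% of all cycles, and about 5% if only completers lack the later count. The effect on per-patient worst-grade rates is smaller, and the documents give no basis for estimating it. The plan supports saying that such cytopenia *may be missed*. It does not support saying that it *will go undetected in every patient*.

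**What to change.** - Mark the blood count, differential and platelet row at End of Treatment with note 12, in the same draw as the chemistry.
- Reconcile note 12 with the calendar by naming the End of Treatment labs it refers to.
- State that this count is included when worst-grade hematologic toxicity is derived for objective 2.2.3 and section 9.4.

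The cost is one extra tube at a draw the plan already requires, one calendar cell and one form field. No dose or stopping rule changes. Recorded hematologic toxicity may rise slightly. The remedy is partial: End of Treatment labs may fall anywhere in the 4 weeks after the last treatment, so a single count may still miss the nadir.

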**5.6 Duration of Follow-up**

For this protocol, all patients, including those who discontinue protocol therapy early, will be followed for response until progression, even if non-protocol therapy is initiated and for survival for 5 years from the date of randomization. All patients must also be followed through completion of all protocol therapy.

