## 6. Measurement of Effect

### 6.1 Antitumor Effect – Solid Tumors

For the purposes of this study, patients should be re-evaluated for response every 12 weeks. In addition to a baseline scan, confirmatory scans should also be obtained 4 weeks following initial documentation of objective response.

Response and progression will be evaluated in this study using the international criteria proposed by the revised Response Evaluation Criteria in Solid Tumors (RECIST) guideline (version 1.1) [Eur J Ca 45:228-247, 2009]. Changes in the largest diameter (unidimensional measurement) of the tumor lesions and the shortest diameter in the case of malignant lymph nodes are used in RECIST.

The following general principles must be followed:

1. To assess objective response, it is necessary to estimate the overall tumor burden at baseline to which subsequent measurements will be compared. All baseline evaluations should be performed as closely as possible to the beginning of treatment and **never more than four weeks** before randomization.
2. Measurable disease is defined by the presence of at least one measurable lesion.
3. All measurements should be recorded in metric notation by use of a ruler or calipers.
4. The same method of assessment and the same technique must be used to characterize each identified lesion at baseline and during follow-up.

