### 9.3 Statistical Design and Efficacy Monitoring

The primary endpoint of this trial is progression-free survival (PFS). Patient assessments will be made every 3 months.

This study will require a minimum of 138 patients (or a maximum of 145 patients to allow for 5% ineligibility) to be accrued at the rate of roughly 6 patients per month. With 23 months of accrual time and 13 months of follow-up (3 years total study time), this trial will have at least 81% power to detect a difference in median PFS between the treatment arms of 9 versus 14 months (hazard ratio of 0.64) using a two-sided log-rank test at the overall 0.20 significance level. The assumption of 9 months for the temozolamide arm is based on historical data of temozolamide alone and temozolamide-based regimens as described in the introduction. The assumption of 14 months for the combination arm is based a goal of improving treatment by 55% (which conservatively approximates the Strosberg PFS data of 18 months).

There will be two log-rank tests conducted, an interim analysis at 76% information (at 80 PFS events, projected to occur just after the end of the accrual period at 26 months) and a final analysis at 100% information (105 PFS events), projected to occur at 3 years from the start of accrual. The overall type I error will be controlled using an O'Brien-Fleming boundary function. Using this boundary, if the repeated two-sided 95% confidence interval on the hazard ratio does not contain the target alternative hazard ratio of 0.64, consideration will be given to declaring the study negative and reporting the results. If the interim log-rank test is positive, the study can be reported early before the projected end of the follow-up period.

Response rate (RR) will be a secondary endpoint. RR will be defined by revised RECIST criteria version 1.1 and include complete responses and partial responses. Prior studies of single agent temozolomide suggest that the response rate associated with single-agent temozolomide is 8-24%; however, overall response rates associated with other temozolomide-based regimens in this disease are between 30-40%. For the purposes of this study, we assume that single agent temozolomide will be associated with a response rate of 33%. Retrospective series of temozolomide/capecitabine have reported response rates of 59-70% in advanced pancreatic neuroendocrine tumors.

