### 10.1 Standard-of-Care Imaging Time Points and Minimum Preferred Phases

Rev. 6/14

- 10.1.1 All standard-of-care imaging studies (including CT, MRI, PET, perfusion CT, or any combination) of the abdomen and pelvis, including all phases completed, will be submitted to ACRIN per Section [10.2](#) instructions. Submission of chest images is optional.
- 10.1.2 Standard practice imaging studies for the trial per E2211 procedures include:
  - Pre-treatment baseline scan for eligibility assessment;
  - Imaging studies during study-prescribed treatment—(e.g. CT scans or MRIs at the completion of cycles 3, 6, 9, and 12 (approximately every 12 weeks)).
  - Follow-up imaging studies—e.g. CT scans or MRIs approximately every 3 months for 3 years from randomization and 6 months for 3-5 years from randomization or until disease progression.
- 10.1.3 Preferably, a minimum of three (3) image phases will be submitted (see below), as well as any perfusion CT sequences that may be performed as standard institutional practice:
  - Preferred:
    - Late arterial phase through the abdomen;
    - Portal venous phase through the abdomen and pelvis;
    - Delayed (equilibrium) phase through the abdomen at 3 to 4 min after contrast administration;
  - If performed per standard institutional practice:
    - Perfusion CT sequences of an area of interest is optional and should be performed according to site specific specifications if available at the participating institution.

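### On-treatment scans follow cycle count and may slip to 16 weeks; if cycle delays differ by arm, the primary PFS comparison shifts slightly towards the more delayed arm

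*Combined protocol and SAP*

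**What the plan says.** Footnote 13 to the study calendar (Section 7.1) sets the on-treatment rule: "the CT scan or MRI, Tumor Measurements, and Tumor Markers will be completed every 3 cycles". If that interval is delayed or extended, "the next interval scan and tumor markers should be completed no more than 16 weeks from previous scan", which is up to 4 weeks beyond the planned 12. Section 10.1.2 also counts in cycles: "CT scans or MRIs at the completion of cycles 3, 6, 9, and 12 (approximately every 12 weeks".

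Two other sections count in calendar time. Section 6.1 says "patients should be re-evaluated for response every 12 weeks", and Section 9.3 says "Patient assessments will be made every 3 months". Once treatment ends, the schedule runs from randomization: "Post treatment scans will be performed every 3 months for 3 years from randomization" (footnote 7).

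The protocol expects cycles to slip. Footnote 4 allows that "the start of each treatment cycle may be scheduled up to three days after the expected Day 1 of that cycle", Sections 5.3.2 and 5.3.3 hold drug until toxicity recovers, and Section 5.3.1 ends treatment only after more than 4 weeks off from the next planned cycle start.

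PFS is the primary endpoint and is compared by a log-rank test (Section 9.3). The documents supplied do not define the PFS event date. Nor do they give an interval-censored or scheduled-visit-date sensitivity analysis, or reporting of scan intervals by arm.

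**The concern.** Progression between scans is normally dated at the scan that shows it. I assume that here, because Section 6.1.4.5 dates the end of response that way. A patient whose scans come later then has a later recorded progression for the same underlying disease course. If this happens equally in both arms, it adds noise but no bias. If it happens more in one arm, that arm's PFS curve moves to the right and the log-rank test reads the movement as benefit.

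A difference between arms is plausible. Only Arm B has capecitabine holds for mucositis, diarrhea and hand-foot rash (Section 5.3.3). It is not established. The neutrophil and platelet levels that trigger a hold are the same for both drugs. A capecitabine hold also need not move the next cycle, since Section 5.3.1 says missed doses are not made up. More delay in Arm A would reverse the direction.

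At stake is the direction of error in the primary comparison. A two-sided 0.20 test already allows a 10% chance of a false finding in favour of the combination, and this mechanism could raise it.

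**Working it through.** **Inputs from the documents.** 138 patients, 69 per arm; 23 months of accrual and 13 of follow-up; medians 9 and 14 months (HR 0.64); final analysis at 105 PFS events; log-rank at two-sided 0.20; interim look at 80 events (all Section 9.3). Scan rules are from Section 7.1, footnotes 4, 7 and 13. Treatment starts within ten working days of randomization (Section 4).

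**The plan's own figures.**

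- Fixed-design power is Φ(½√105 × |ln HR| − 1.2816), with ½√105 = 5.123. HR 0.64 gives Φ(2.287 − 1.282) = 84.3%; the ratio 9/14 gives 83.7%.
- A two-look O'Brien-Fleming boundary at 80/105 information lowers these to 82.6% and 82.0%, consistent with the stated minimum of 81%.
- Expected events at 36 months under exponential PFS are 69 × {1 − [exp(−13λ) − exp(−36λ)]/(23λ)} per arm, with λ = ln 2/median. This gives 57.1 + 47.4 = 104.5, against 105 stated.

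**What a small shift in the HR does to the error.** With 105 events and no true effect, the mean of the log-rank z is about 5.123 × ln(HR).

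| Apparent HR | Mean z | False win for B | False win for A | Two-sided |
|---|---|---|---|---|
| 1.00 | 0 | 10.0% | 10.0% | 20.0% |
| 0.99 | −0.051 | 10.9% | 9.1% | 20.1% |
| 0.98 | −0.104 | 11.9% | 8.3% | 20.2% |
| 0.96 | −0.209 | 14.2% | 6.8% | 21.0% |
| 0.95 | −0.263 | 15.4% | 6.1% | 21.5% |

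The two-sided error hardly moves because error is transferred from one side to the other.

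**How large a shift scan timing can cause.** The delay rates are assumptions. The main simulation used exponential PFS with median 9 months in both arms, four on-treatment scans with the interval capped at 16 weeks, then scans every 3 months from randomization. It dated 90% of events at the next scan and 10% exactly. It used 20,000 trials per case (standard error about 0.2 points) and a single look at 105 events. Percentages are shares of patients with some intervals 1 to 4 weeks late.

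| Case | HR | False win for B | Two-sided |
|---|---|---|---|
| No delay | 1.000 | 10.2% | 20.3% |
| Equal, 30% v 30% | 1.003 | 10.1% | 20.2% |
| A 20%, B 40%, up to 2 intervals | 0.992 | 10.7% | 20.3% |
| A 20%, B 50%, up to 2 intervals | 0.988 | 11.5% | 20.5% |
| A 10%, B 70%, up to 4 intervals | 0.981 | 12.0% | 20.5% |
| Reversed, A 50%, B 20% | 1.010 | 9.5% (A: 11.2%) | 20.7% |
| Every B interval 14 weeks, A 12 | 0.951 | 15.1% | not listed |
| Every B interval 16 weeks, A 12 | 0.995 | 10.4% | not listed |
| Calendar scans, ±1 week, both arms | 1.000 | 10.2% | 20.0% |

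Power at 9 v 14 months was 82.8% with no delay and 83.1% with calendar scans.

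**Sensitivity to the delay model.**

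- Holds of 1 to 2 weeks per cycle, in 10% of Arm A cycles and 20 to 30% of Arm B cycles, give mean scan intervals of about 12.4 v 12.9 to 13.3 weeks. The null HR is 0.97 to 0.96, the false-win rate for B 13 to 14%, and the two-sided error 20.5 to 21%. Under 9 v 14 months the HR moves from 0.64 to 0.62–0.63 and apparent power from 83% to 86–87%.
- No delay in Arm A and 25 to 100% of Arm B intervals late by 1 to 4 weeks gives HR 0.94 to 0.98, false wins for B of 12 to 17%, and two-sided error of about 20 to 23%.
- More delay in Arm A than in Arm B, in the same per-cycle model, gives a null HR of 1.02 and power of 80%.

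**The case against.** The strongest reply is that the effect is small and its premise is assumed. The planned test is two-sided, and under partial unequal delay that error stays within about a point of 20%. No delay rates appear in the documents, and Section 5.3.1 lets Arm B patients stop one agent and continue the other, which weakens the link between capecitabine toxicity and late scans. Footnote 13 is itself a safeguard because it caps the interval. Patients off treatment too long must discontinue, after which they have an end-of-treatment scan, unless a recent one exists, and move to calendar-based scans. Adding discontinuation and that scan to the simulation left the HR at 0.979 to 0.993 and the two-sided error at 20.0 to 20.3%. The size also depends on how the two scan grids line up: it is larger at a fixed 14 weeks than at 16. Finally, three 28-day cycles are 12 weeks, so the sections agree nominally.

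Most of this stands. The shift is small and conditional, and no single range for it is firm. Two parts do not dispose of the point. The cap limits the shift without removing it. The nominal agreement between sections holds only while cycles run on time, which is exactly when the problem does not arise.

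The reply is also right that a ±1 week window is tighter than the present tolerance and may produce more recorded deviations, and that tumor markers should not be separated from the scans.

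**Conclusion.** The concern holds as a conditional, modest bias in the primary endpoint. Cycle-based scanning lets treatment delay influence when progression is recorded, and nothing in the documents supplied offsets this if delay differs by arm. The more delayed arm gains. Plausible unequal delay gives a null HR of about 0.96 to 0.99 and a false-win rate of 10.5 to 14%, against 10%. Extreme patterns reach 0.94 and about 17%. The two-sided error is almost unchanged in the plausible cases and at most about 23% in the extreme ones.

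These figures rest on assumed delay rates, exponential PFS, progression dated at the scan that shows it, and a single final look. That delays will differ between these arms, and in which direction, cannot be known from the documents. Equal delay or calendar scans remove the shift, so the case for change is that prevention is cheap.

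**What to change.** In the Section 7.1 calendar and footnote 13, replace the every-third-cycle rule for CT/MRI and tumor measurements with scans every 12 weeks counted from randomization while on treatment. Use one symmetric window in both arms (for example ±1 week), regardless of held or delayed cycles. Keep the tumor markers with the scans. Bring Sections 6.1, 9.3 and 10.1.2 to the same wording.

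Leave unchanged the post-treatment schedule in footnote 7 and the rule in Section 5.6 that patients "will be followed for response until progression, even if non-protocol therapy is initiated". No dose or hold rule needs to change.

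As a supplement, report scan intervals by arm and add a PFS sensitivity analysis using interval censoring or scheduled visit dates. This would also serve as the fallback if the schedule cannot be changed.

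The cost is protocol wording and site scheduling. Frequency, procedures and power (about 83% simulated) stay as they are. Some scans will not coincide with a cycle visit, and a narrower window will probably yield more recorded deviations; a wider window is acceptable if it is the same in both arms.
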